9.7 PHARMACODYNAMICS

CD19+ cell count and total IgG and IgM levels (as well as change from baseline) will be summarized descriptively by treatment and visit. The percent of subjects with complete depletion of CD19+ cell count from baseline to day 8, week 3, week 4 and week 28 will also be summarized descriptively by treatment.

9.8 SAFETY ANALYSES

All safety analyses will be performed on the safety analysis set based on a subject's actual treatment received.

9.8.1 Adverse Events

All reported AEs will be coded to the appropriate SOC and PT according to the most current version of MedDRA, and the severity of each AE will be graded by the investigator per CTCAE v4.03 criteria.

Subject incidence of treatment-emergent AEs will be tabulated by treatment groups and by SOC, PT, and maximum severity grade per CTCAE v 4.03. Subject incidence of treatment-emergent AEs will also be summarized by SOC and PT.

Subject incidence of the following AEs will be tabulated by preferred term in descending order of frequency in the ABP 798 arm:

- treatment-emergent AEs
- \geq Grade 3 treatment-emergent AEs
- treatment-emergent AEs leading to discontinuation of IP
- treatment-emergent AEs leading to dose delay of IP
- each treatment-emergent event of interest category

Infusion reaction and tumor lysis syndrome EOIs will also be summarized by PT and maximum CTCAE grade.

Subject incidence of treatment-emergent AEs by PT in descending order of frequency in the ABP 798 arm and by SOC and PT will be also tabulated by gender, age (<65 vs. \geq 65), race (White vs. non-White), and region (Eastern Europe vs. Western Europe/Other vs. North America vs. Japan).

AEs leading to discontinuation of IP are those with an action taken with Investigational Medicinal Product of “dose discontinued”. AEs leading to delay of IP are those with an action taken with Investigational Medicinal Product of “dose delayed”.

Counting of AEs will be by subject, and subjects will be counted only once within each SOC or PT. For tables categorized by severity, subjects with multiple events within a particular SOC or preferred term will be counted under the category of their most severe event within that SOC or preferred term.

Exposure-adjusted AE incidence rates per 100 patient-years (p-y) will also be calculated for all treatment-emergent AEs. The exposure-adjusted incidence rate per 100 p-y is the number of subjects who experience an event divided by the total subject exposure time multiplied by 100.

Subjects with AEs leading to discontinuation of study therapy will be listed.

9.8.2 Fatal and Serious Adverse Events

Subject incidence of serious treatment-emergent AEs will be tabulated by treatment groups and by SOC, PT, and maximum severity grade per CTCAE v 4.03.

Subject incidence of the following AEs will be tabulated by preferred term in descending order of frequency in the ABP 798 arm:

- serious treatment-emergent AEs
- fatal AEs (AEs with a severity grade of 5 and/or outcome of fatal)

Subjects with serious AEs will also be listed.

9.8.3 Laboratory Data

Laboratory test results will be reported in International System of Units (SI) units.

Laboratory values and change from baseline will be summarized using descriptive statistics for each IP dose by treatment. For each IP dose, the lab assessment summarized will be the assessment closest to the date of IP dose and contained in the window of (IP dose date – 3 days) to IP dose date, inclusive. Shift tables of the minimum and maximum post-baseline values based on CTCAE v4.03 grading relative to baseline will be presented by treatment group for parameters that have CTCAE criteria. Shift tables will include all laboratory assessments. In addition, subject incidence tables and listings of Grade ≥ 3 laboratory toxicities will be provided. Standard ranges will be used for the laboratory analysis.

Lab assessments will be grouped for summary as follows:

- Hematology – white blood cell parameters: white blood cell count and absolute neutrophil count
- Hematology – red blood cell parameters: hemoglobin and packed cell volume or hematocrit
- Hematology – other parameters: platelets
- Serum chemistry – hepatobiliary parameters: alanine aminotransferase, aspartate aminotransferase, total bilirubin, alkaline phosphatase, lactate dehydrogenase
- Serum chemistry – general chemistry: sodium, potassium, albumin, total protein, non-fasting glucose
- Serum chemistry – renal function tests: urea, creatinine, blood urea nitrogen, uric acid

9.8.4 Vital Signs

Vital sign assessments include blood pressures (diastolic and systolic), pulse, respiration rate, and temperature. Change from baseline in vital signs will be summarized by treatment group. Descriptive statistics will be shown for baseline, the result at each IP dose, and the change from baseline to each IP dose result. For each IP dose, the vitals assessment summarized will be the assessment closest to the date of IP dose and contained in the window of (IP dose date – 3 days) to IP dose date, inclusive.

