Safety endpoints will be summarized descriptively as well. Subgroup analyses (by gender, race, and stratification factors as appropriate) may be presented. Safety will be assessed in the safety analysis set with treatment assignment based on actual treatment received. All verbatim terms for any reported AEs will be coded to the appropriate system organ class and preferred term according to the current version of the Medical Dictionary for Regulatory Activities dictionary, and graded by the Investigator for severity as per Common Toxicity Criteria for Adverse Events version 4.03. The number and percentage of subjects reporting AEs (all, serious, related, and deaths), and developing antidrug antibodies will be tabulated by treatment. Vital signs and laboratory data will also be summarized descriptively by visit and treatment. The safety endpoints of PFS and OS will be analyzed including all events up to the time of the last subject's end-of-study visit. Median PFS and OS time and survival curves may also be estimated using Kaplan-Meier methods. Descriptive 1-sided 95% and 97.5% CIs on the hazard ratios of PFS and OS will be estimated based on Cox models, stratified by stratification factors.

Independent safety reviews will be performed by the DMC periodically throughout the study, including an initial safety review after the first 12 subjects have received at least 2 doses of IP. Blinded study data will also be monitored on an ongoing basis by the blinded clinical study team to ensure subjects' safety.

DATE AND VERSION: 5.0, 17 July 2017

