9.6 Week 28/End of Study

For subjects completing the treatment phase, the EOS visit will be at week 28, 8 weeks (± 7 days) after the last dose of IP. For subjects who do not complete the treatment phase, the EOS visit will be 8 weeks (± 7 days) after the last dose of IP. **Subjects who discontinue from the study due to disease progression should have a CT scan (as described below) prior to initiation of new anti-cancer treatment, if deemed clinically acceptable.**

At the EOS visit (**week 28 or 8 weeks after the last dose of IP**), the following assessments will be performed:

- physical examination, including evaluation of body systems
- vital signs (systolic and diastolic blood pressure, pulse, respiration rate, and temperature)
- standard 12-lead ECG
- ECOG performance status
- clinical disease assessment
- CT (not required if performed within the previous 4 weeks) of the neck (if palpable lymph node >1.0 cm or if performed at baseline), chest, abdomen, and pelvis.
- bone marrow biopsy (only required if bone marrow involvement is identified at baseline **for CR confirmation; if a confirmatory bone marrow assessment is not obtained, these subjects should be considered as only having a PR**). **The bone marrow biopsy can be performed at ± 14 days in relation to the study visit date.**
- clinical laboratory testing, including serum chemistry and hematology
- collection of samples for PK, antidrug antibodies, CD19+ cell count, and IgG and IgM levels

Any changes in concomitant medications since the last assessment will be recorded.

Any additional treatment for lymphoma will be recorded. All AEs, including increases in severity or frequency of pre-existing conditions, will be recorded in the eCRF through the week 28 visit. SAEs will be reported as outlined in [Section 11.2.2](#). Any SAEs ongoing at week 28 will be followed until they resolve or are considered chronic or stable.

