12.6.7.6 Clinical Laboratory Test

Clinical laboratory test results and change from baseline will be summarized by time point. In addition, shift tables, from baseline to the worst on-study laboratory toxicity based on CTCAE v4.03 grading, will be presented.

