12.6.7.7 Vital Signs and Physical Examinations

Vital sign data (observed and change from baseline) will be summarized using descriptive statistics by time point and treatment. Abnormal findings from physical examinations will be listed by subject and assessed for clinical significance and included in the AE listings and summaries.

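### SAP 9.8.3 and 9.8.4 tie laboratory and vital-sign summaries to IP doses, so week-28/EOS values cannot enter them: a complete gap for vital signs, a partial one for laboratory data

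*SAP*

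**What the plan says.** **Protocol.** The Synopsis (Statistical Methods) states: "Vital signs and laboratory data will also be summarized descriptively by visit and treatment". Section 12.6.7.6 adds: "Clinical laboratory test results and change from baseline will be summarized by time point". Section 12.6.7.7 says that vital-sign data, observed and change from baseline, "will be summarized using descriptive statistics by time point and treatment". Table 1 and Section 9.6 schedule vital signs, serum chemistry and hematology at the end-of-study visit. On timing, Section 9.6 says: "For subjects completing the treatment phase, the EOS visit will be at week 28", which it places 8 weeks (± 7 days) after the last dose. The same interval applies to subjects who stop early. No IP is given at that visit.

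**SAP.** Section 9.8.3 states: "Laboratory values and change from baseline will be summarized using descriptive statistics for each IP dose by treatment". Section 9.8.4 states: "Descriptive statistics will be shown for baseline, the result at each IP dose, and the change from baseline to each IP dose result". It adds that, for each dose, "the vitals assessment summarized will be the assessment closest to the date of IP dose", within the 3 days before it or on the day itself; Section 9.8.3 applies the same rule to laboratory values. Section 9.8.3 then adds, for laboratory data only: "Shift tables will include all laboratory assessments". It also plans incidence tables and listings of Grade 3 or higher results. Section 9.8.4 has no counterpart for vital signs.

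**SAP Appendix 3.** Tables 14-7.1.1 to 14-7.1.3 (hematology), 14-7.2.1 to 14-7.2.3 (chemistry) and 14-8.3 (vital signs) are all titled by IP dose. Table 14-8.3 is the only vital-sign output listed.

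**The concern.** The SAP rule does more than leave a detail open. It selects values by distance from a dose, and so shuts out a visit at which the data are scheduled to be collected. The SAP treats week 28 differently elsewhere: Section 9.7 reports CD19+ depletion at week 28, and Section 9.8.8 summarises ECG at week 28/EOS. No reason is given for handling laboratory values and vital signs otherwise.

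Apart from same-day monitoring around the infusion, EOS is the only scheduled laboratory and vital-sign assessment after the last dose. Clinically significant changes in these measures are a listed safety endpoint (Protocol 8.6.1.3, SAP 4.2.4). As written, the report would hold no side-by-side description of the arms at EOS for vital signs, and no mean or change from baseline there for laboratory values.

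**Working it through.** The plan gives no figure of its own to reproduce. The check is a comparison of dates, a count of visits, and a reading of the listed outputs.

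**1. Can an EOS value fall in the window?**
- Window, SAP 9.8.3 and 9.8.4: day −3 to day 0 relative to an IP dose.
- EOS, Protocol 9.6: 8 weeks ± 7 days after the last dose = 56 ± 7 = day 49 to day 63.
- The overlap of {−3, …, 0} and {49, …, 63} is empty. Earlier doses lie further away, and no dose follows EOS. The result is the same for completers and for early discontinuers.

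**2. How many time points are lost?**
- Scheduled post-baseline laboratory and vital-sign points, Protocol Table 1: weeks 2, 3, 4, 12, 20 and 28 = 6.
- Points with a planned dose, Protocol 8.3: weeks 2, 3, 4, 12 and 20 = 5.
- Lost for a subject who receives every dose: 6 − 5 = 1, and 1/6 = 16.7%.
- With an EOS row added, all 6 are covered.

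**3. Which listed outputs still carry EOS?**

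| Output (SAP 9.8.3, 9.8.4, Appendix 3) | EOS included? |
|---|---|
| Hematology values and change, 14-7.1.1 to 14-7.1.3 | No |
| Chemistry values and change, 14-7.2.1 to 14-7.2.3 | No |
| Laboratory shift tables, 14-7.1.4 and 14-7.2.4 | Yes, all assessments are used |
| Grade 3 or higher laboratory tables and listings | Yes, as nothing limits them to dose dates |
| Vital signs, 14-8.3 | No |
| Any other vital-sign table or listing | None listed |

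Tables that lose EOS: 3 + 3 + 1 = 7.

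**4. What do the remaining laboratory outputs show?** The shift tables give the minimum and maximum post-baseline values by CTCAE grade, for parameters that have CTCAE criteria. An EOS value appears there only if it is the extreme, and the table does not say when the extreme occurred. They therefore cover part of what is lost, but do not describe the arms at EOS.

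**The case against.** **The protocol conflict is narrow.** Only the Synopsis says by visit. Sections 12.6.7.6 and 12.6.7.7 say by time point without promising every scheduled visit, planned doses map one-to-one onto visits 1 to 6, and Section 12.3 leaves detailed methods to the SAP. This stands as far as it goes: by-dose tables are a defensible layout for visits 1 to 6. It does not explain why the remaining scheduled time point has no place.

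**The consequence is small.** The endpoint is clinically significant change, not mean change. Protocol 10.4 and 10.6 send clinically relevant findings to adverse event reporting, which runs through EOS. This also stands, and it bounds the importance of the point. It does not close the vital-sign gap, because an EOS value then appears only when an investigator judges it reportable.

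**The documents are incomplete.** The shells are a separate document (SAP Appendix 4). The SAP is version 1.1, written to protocol version 3.0, which is not to hand. An EOS row may already exist in the shells. If so, the SAP text would still lack a rule for choosing the value.

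Several stronger readings are tempting but are not supported:
- *Week-28 laboratory data disappear from the report.* They do not; see the shift tables and Grade 3 or higher outputs.
- *The loss is larger for subjects who stop early, so the overall loss is large.* The documents give no discontinuation rate, so no overall size can be stated.
- *The whole final 8 weeks go unsummarised.* Weeks 4 to 12 and 12 to 20 are also 8-week intervals with no scheduled laboratory or vital-sign assessment in between. What is lost is one assessment.
- *Visits attended without a dose are lost too.* Protocol 8.5.6.1 defines a missed dose by its delay; it does not say that the subject attends and is assessed undosed.

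**Conclusion.** The concern holds in a limited form. Under the SAP text, scheduled week-28/EOS values cannot enter the by-dose summaries for any subject. The gap is complete for vital signs in the listed outputs and partial for laboratory data. The loss is one time point in seven descriptive tables. The date result needs no assumption beyond the stated EOS timing; the one-in-six count assumes a subject who receives all doses and attends as scheduled; the statement about outputs rests on the Appendix 3 titles.

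A reader might infer that the biosimilarity conclusion is weakened. It is not: SAP 9.5.3 confines inference to the primary endpoint, and no margin, test or decision depends on these tables. This is worth correcting before database lock because it is cheap, not because it threatens the trial.

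**What to change.** In SAP2, amend Sections 9.8.3 and 9.8.4 to add an EOS time point, with value and change from baseline by arm:

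1. Add it to table 14-8.3 first, since no other listed output covers vital signs at EOS. Then add it to tables 14-7.1.1 to 14-7.1.3 and 14-7.2.1 to 14-7.2.3.
2. State the selection rule: use the assessment recorded at the EOS visit, for completers and early discontinuers alike.
3. Label the row Week 28/EOS (8 weeks after last dose). It pools subjects with different numbers of doses, so either show the number of early discontinuers in it or also present completers separately.
4. Check the table shells and bring them into line with the amended text.

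The cost is one row (two if completers are shown separately) in seven existing tables and a sentence in each SAP section. The assessments are already scheduled, SAP Section 1 already plans SAP2 before database lock, and no visit, test or inference is added.

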9.8.5 Immunogenicity

The number and percentage of subjects developing binding and neutralizing ADA will be tabulated for each treatment. Pre-existing antibody incidence (on or before the first dose of study IP) and developing antibody incidence will be summarized. Pre-existing antibody incidence is defined as the number of subjects with a positive antibody result at baseline divided by the number of subjects with an immunoassay result at baseline. Developing antibody incidence is defined as the number of subjects with a negative or no antibody result at baseline and a positive antibody result at a post-baseline time point divided by the number of subjects with at least one

post-baseline immunoassay result. A transient antibody result is defined as a positive post-baseline result with a negative result at the subject's last timepoint tested within the study period.

9.8.6 Progression-free Survival

The primary analysis of PFS will be based on disease assessments determined by the central, independent, blinded radiologists' and oncologist's review.

The LIFETEST procedure in SAS[®] will be used to produce estimates of quartiles and 95% CIs via the method of [Brookmeyer and Crowley \(1982\)](#) and to produce KM survival plots. The standard error of the KM quartile estimates will be estimated using Greenwood's formula ([Kalbfleisch and Prentice, 1980](#)).

Estimates of the hazard ratio (HR) for treatment and the corresponding 1-sided 95% and 97.5% CIs will also be presented. They will be estimated using the stratified Cox proportional hazards regression model using the PHREG procedure in SAS[®]. The model will be stratified by the randomization stratification factors. HRs will be calculated using the rituximab arm as the reference group.

Progression-free survival will also be summarized based on the investigator assessment of progression.

9.8.7 Overall Survival

The analyses of OS will be performed per the analyses for PFS (see [Section 9.8.6](#)).

9.8.8 Electrocardiogram

The standard 12-lead electrocardiogram results at baseline and week 28/EOS visit will be summarized as normal, abnormal - clinically significant, or abnormal - not clinically significant.

9.9 ANALYSES FOR JAPAN

For Japan, the evaluation of equivalence of efficacy will be based on a 2-sided 95% CI for the RD of ORR.

Subject disposition, demographic and study baseline characteristics, IP exposure, and key efficacy and safety endpoints will be summarized for the subgroup of Japanese subjects.

10. VALIDATION

PRA seeks to ensure the quality of the results provided for the study in the form of TFLs, and the derived datasets used in their creation, through the following processes:

- Derived datasets are independently reprogrammed by a second programmer. The separate datasets produced by the two programmers must match 100%. Detailed

specifications for the derived datasets are documented and the documentation is provided to the client at study conclusion.

- Tables are independently reprogrammed by a second programmer for numeric results.
- Figures are checked for consistency against corresponding tables and listings, or independently reprogrammed if there are no corresponding tables or listings.
- Listings are checked for consistency against corresponding tables, figures, and derived datasets.

The entire set of TFLs is checked for completeness and consistency prior to its delivery to the client by the lead clinical programmer, the lead statistician, and a senior level statistician, or above, who is not a member of the project team.

The PRA validation process is repeated any time TFLs are redelivered using different data. Execution of this validation process is documented and the documentations is provided to the client at study conclusion.

APPENDIX 1 GLOSSARY OF ABBREVIATIONS

Glossary of Abbreviations:	
ADA	Anti-drug Antibody
ADaM	Analysis Data Model
AE	Adverse Event
CDISC	Clinical Data Interchange Standards Consortium
CI	Confidence Interval
CIOMS	Council for International Organizations of Medical Sciences
CR	Complete Response
CRu	Complete Response Unconfirmed
CT	Computed Tomography
CTCAE	Common Terminology Criteria for Adverse Events
CTMS	Clinical Trials Management System
DMC	Data Monitoring Committee
ECOG	Eastern Cooperative Oncology Group
eCRF	Electronic Case Report Form
EDC	Electronic Data Capture
EOI	Event of Interest
EOS	End of Study
FAS	Full Analysis Set
FLIPI	Follicular Lymphoma International Prognostic Index
GMR	Geometric Mean Ratio
HR	Hazard Ratio
IgG	Immunoglobulin G
IgM	Immunoglobulin M
IP	Investigational Product
IV	Intravenous
IXRS	Interactive Voice/Web Response System

KM	Kaplan-Meier
MedDRA	Medical Dictionary for Regulatory Activities
NCI	National Cancer Institute
NHL	Non-Hodgkin's Lymphoma
ORR	Overall Response Rate
OS	Overall Survival
PD	Progressive Disease
PDV	Protocol Deviations and Violations
PFS	Progression-free Survival
PK	Pharmacokinetic
PP	Per Protocol
PR	Partial Response
PT	Preferred Term
P-Y	Patient-Year
Q1	25 th Percentile
Q3	75 th Percentile
RD	Risk Difference
SAE	Serious Adverse Event
SAP	Statistical Analysis Plan
SD	Stable Disease
SDTM	Standard Data Tabulation Model
SI	International System of Units
SMQ	Standard MedDRA Query
SOC	System Organ Class
SPD	Sum of the Products of the Greatest Diameters
TFL	Tables, Figures, and Listings
WHO-DD	World Health Organization Drug Dictionary

APPENDIX 2 RESPONSE DETERMINATION BY IWG (1999)

CRITERIA

Responses will be categorized as complete response (CR), CR/unconfirmed, partial response (PR), stable disease (SD), or progressive disease (PD). In addition, a response category of not evaluable (NE) is provided for situations in which there is inadequate information to otherwise categorize response status.

11.1 COMPLETE RESPONSE

To satisfy criteria for CR, all of the following criteria must be met:

1. Complete disappearance of all detectable clinical and radiographic evidence of disease and disappearance of all disease-related symptoms if present before therapy, and normalization of those biochemical abnormalities (eg, lactate dehydrogenase) definitely assignable to NHL.
2. All lymph nodes and nodal masses must have regressed to normal size (≤ 1.5 cm in their greatest transverse diameter for nodes > 1.5 cm before therapy). Previously involved nodes that were 1.1 to 1.5 cm in their greatest transverse diameter before treatment must have decreased to ≤ 1 cm in their greatest transverse diameter after treatment, or by more than 75% in the sum of the products of the greatest diameters (SPD).
3. The spleen, if considered to be enlarged before therapy on the basis of a CT scan, must have regressed in size and must not be palpable on physical examination. However, no normal size can be specified because of the difficulties in accurately evaluating splenic and hepatic size. For instance, spleens thought to be of normal size may contain lymphoma, whereas an enlarged spleen may not necessarily reflect the presence of lymphoma but variations in anatomy, blood volume, the use of hematopoietic growth factors, or other causes. Any macroscopic nodules in any organs detectable on imaging techniques should no longer be present. Similarly, other organs considered to be enlarged before therapy due to involvement by lymphoma, such as liver and kidneys, must have decreased in size.
4. If the bone marrow was involved by lymphoma before treatment, the infiltrate must be cleared on repeat bone marrow aspirate and biopsy of the same site. The sample on which this determination is made must be adequate (≥ 20 mm biopsy core).

